8.2 Sample size estimate

The study will recruit approximately 175 patients with T790M mutation positive advanced NSCLC, whose disease has progressed following either one prior therapy with an EGFR-TKI (chemotherapy-naïve, n=50) or following treatment with both EGFR-TKI and a platinum-based doublet chemotherapy (Patients may have also received additional lines of treatment,

n=125). With 175 patients the precision of the estimation of ORR in the overall study population will be within +/-8% (e.g. ORR 40%, 95% CI 33.0%, 47.4%). The precision of the estimation of ORR will be within +/-13% in the 50 patient cohort who have only received previous TKI treatment and within +/-9% in the 125 patient cohort who have received previous treatment with both an EGFR-TKI and a platinum-based doublet chemotherapy. The study will also provide an adequate number of patients in which to assess the safety and tolerability of AZD9291; if zero events are observed in the 175 patients, there is 95% confidence that the true event rate is less than 2.2%.

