1.5 Study design

This is a phase II, open label, single arm study assessing the safety and efficacy of AZD9291 (80 mg, orally, once daily) in patients with a confirmed diagnosis of EGFRm+ and T790M+ locally advanced or metastatic NSCLC (Stage IIIB-IV), who have progressed following prior therapy with an approved EGFR-TKI agent.

In order to enrol approximately 175 patients it is expected that approximately 440 patients will be screened. Patient enrolment will consist of 2 cohorts:

- Approximately 50 patients with T790M+ NSCLC who have progressed following 1st line EGFR-TKI treatment but who have not received further treatment
- Approximately 125 patients with T790M+ NSCLC who have progressed following prior therapy with an EGFR-TKI and a platinum-based doublet chemotherapy. Patients may have also received additional lines of treatment.

[figure not shown]
The study size has been selected in order to make an accurate assessment of safety/tolerability and to estimate ORR with 95% confidence intervals that are within +/- 8%. The sample size of each cohort has been selected in order to provide precision of the estimation of ORR (+/- 9% for multiple therapies; +/-13% for previous TKI only). Enrolment to individual cohorts may be closed separately. Sites will be informed in advance of cohort closure timelines.

A mandatory biopsy will be needed for central testing of T790M mutation status following confirmed disease progression on the most recent treatment regimen. The T790M mutation status of the patient's tumour must be determined by the designated central laboratory using the cobas[®] EGFR Mutation Test (Roche Molecular Systems).

Patients should continue on treatment with AZD9291 until RECIST 1.1 defined progression or until a treatment discontinuation criterion is met. There is no maximum duration of treatment

as patients may continue to receive AZD9291 beyond RECIST 1.1 defined progression as long as they are continuing to show clinical benefit, as judged by the investigator.

Figure 1 Study Flow Chart

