8.9.1 Analysis of the primary variable(s)

Objective response rate (ORR) by ICR in the evaluable for response analysis set will be presented together with 95% exact (Clopper Pearson) confidence intervals. Summaries of the number of patients with best response in each of the follow categories will be summarised: Complete Response (CR), Partial Response (PR), Stable Disease (SD), Progressive Disease (PD) and Non-Evaluable (NE).

The baseline patient characteristics will be summarised, including demographics, EGFR mutation type and prior anti-cancer therapy, including most recent previous treatment.

Additional summaries of ORR will be performed

- ORR by investigator assessment
- ORR summarised for both confirmed and unconfirmed responses
- ORR by EGFR mutation subtype: Exon 19 deletion/L858R/Other.
- ORR in the subgroup of patients who received TKI as last treatment prior to study start and those whose treatment prior to study start was not a TKI
- ORR at week 6 and 12 will also be summarised.

The concordance between ORR as assessed by ICR and by investigator will be presented.

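### The ±13% ORR precision stated for the 50-patient cohort, and the example interval for 175 patients, are narrower than the exact intervals the plan will report

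*Supplement*

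**What the plan says.** The analysis method is explicit. Section 8.9.1 says that ORR by independent central review "will be presented together with 95% exact (Clopper Pearson) confidence intervals", and the statistical methods in the synopsis also call for exact 95% intervals.

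The planning figures are in three places:

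- Section 8.2 (and the synopsis), 175 patients overall: "within +/-8% (e.g. ORR 40%, 95% CI 33.0%, 47.4" (percent).
- Section 8.2, the two cohorts: "The precision of the estimation of ORR will be within +/-13% in the 50 patient cohort who have only received previous TKI treatment". For the 125 patients previously given a TKI as well as platinum chemotherapy, the figure is ±9%.
- Section 1.5 repeats the cohort figures ("9% for multiple therapies; +/-13% for previous TKI only") and says the cohort sizes were chosen to give that precision.

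No response rate is given for the cohort figures, and the interval method behind the planning figures is not named. Amendments 1 and 2 leave Sections 1.5, 8.2 and 8.9.1 unchanged. Amendment 2 revises the statistical methods in the synopsis, but only the paragraph on the primary data cut-off.

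**The concern.** This is a single-arm estimation study, so for ORR the stated precision is the whole justification for the sample size. A reader is entitled to expect that the planning figures use the interval that will be reported. If they use a narrower one, the published interval will be wider than the protocol promised.

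The 50-patient cohort is where this could show. It is the smallest group, its ORR is to be presented separately, and the method matters most at small numbers. The rates the protocol itself mentions, 40% in the example and 50% from the phase I study (Section 1.3), lie near the middle of the scale, where intervals are widest.

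**Working it through.** **Inputs.** n = 175, 125 and 50 (Section 8.2). Response rates: 40% (example in Section 8.2) and 50% (phase I rate, Section 1.3). Using these rates for the cohorts is an assumption, since none is stated, so the full range was also checked. Two-sided 95% intervals, z = 1.96.

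**Formulas**, for x responders in n, with p = x/n:

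- Clopper-Pearson: lower limit = 2.5% quantile of Beta(x, n − x + 1); upper limit = 97.5% quantile of Beta(x + 1, n − x).
- Wilson: [p + z²/2n ± z√(p(1 − p)/n + z²/4n²)] / (1 + z²/n).
- Half-width = (upper − lower)/2. An arm is the distance from p to one limit.

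**Step 1: reproduce the plan's example, 70/175.**

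Wilson: z²/n = 0.02195 and z²/2n = 0.01098. The root is √(0.24/175 + 0.0000314) = 0.03745, and 1.96 times that is 0.0734. The limits are (0.4110 − 0.0734)/1.02195 = 33.0% and (0.4110 + 0.0734)/1.02195 = 47.4%. This is the printed interval.

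Clopper-Pearson gives 32.7% to 47.7%, so each printed limit is about 0.3 points too close to 40%. The Agresti-Coull and Jeffreys intervals also round to 33.0% to 47.4%, and the simple normal interval does not (32.7% to 47.3%). The match therefore shows that the example is not Clopper-Pearson; it is consistent with Wilson but does not prove it.

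**Step 2: the stated precisions under both methods** (points):

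| n | stated | x/n | Wilson half-width | Clopper-Pearson interval | exact half-width | exact arms |
|---|---|---|---|---|---|---|
| 175 | ±8 | 70/175 | 7.2 | 32.7% to 47.7% | 7.5 | −7.3 / +7.7 |
| 125 | ±9 | 50/125 | 8.5 | 31.3% to 49.1% | 8.9 | −8.7 / +9.1 |
| 50 | ±13 | 20/50 | 13.1 | 26.4% to 54.8% | 14.2 | −13.6 / +14.8 |
| 50 | ±13 | 25/50 | 13.4 | 35.5% to 64.5% | 14.5 | ±14.5 |

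The Wilson half-widths at 40% (7.2, 8.5, 13.1) fit the stated 8, 9 and 13 as whole-number figures.

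**Step 3: worst case over all possible results, Clopper-Pearson.**

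- n = 175: largest half-width 7.6, longest arm 7.7. ±8 holds throughout.
- n = 125: largest half-width 9.07, longest arm 9.16. ±9 holds to rounding.
- n = 50: largest half-width 14.5, longest arm 14.8. ±13 does not hold.

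**Step 4: where ±13 fails for n = 50.** The exact half-width is 12.9 at 13/50 and 37/50, and 13.1 at 14/50 and 36/50. It is above 13 for every count from 14 to 36, that is, observed rates from 28% to 72%.

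**Step 5: scale of the gap.** For both exact limits to lie within 13 points, about 65 patients are needed at 40%, or 62 at 50%. This shows the size of the discrepancy; it is not a case for enlarging the cohort.

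**The case against.** The case for leaving the text alone has real substance. The figures form one coherent set of whole-number Wilson half-widths, so this is one mismatch between planning and analysis method, not several arithmetic slips. The cohort sizes are approximate. The primary estimate is the overall ORR, whose ±8% holds. No hypothesis test, success threshold or interim decision uses these numbers, and the reported intervals will be exact whatever the planning text says. All of that stands and limits the severity. It does not rescue ±13%: 14.2 and 14.5 do not round to 13, and the plan names the exact method.

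Three stronger readings are tempting, and the documents do not support them.

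- **Both cohort sizes rest on unattained precision.** They do not. For 125 patients the exact half-width is 8.9 at 40% and never above 9.07. Only the longer arm of an asymmetric interval passes 9, by less than 0.2 points.
- **The zero-event safety bound is also wrong.** Section 8.2 says that with no events in 175 patients "there is 95% confidence that the true event rate is less than 2.2"%. The exact upper bound is 1 − 0.05^(1/175) = 1.7% one-sided, or 1 − 0.025^(1/175) = 2.1% two-sided. Both are below 2.2%, so the statement is true and conservative. Clopper-Pearson is in any case specified for ORR, not for adverse event rates.
- **Precision is overstated further because ORR is analysed in evaluable patients, not all enrolled.** Section 8.3.2 does require measurable disease by independent review, but inclusion criterion 9 already requires a measurable lesion, and no expected loss is given. Any loss would widen the intervals somewhat; its size cannot be taken from the documents.

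**Conclusion.** Wrong as written, minor. Two statements do not agree with the specified exact method: the example interval for 175 patients, by about 0.3 points at each limit, and the ±13% for the 50-patient cohort. The latter is optimistic by 1.2 points of half-width at 40% (14.2 − 13) and 1.5 at 50% (14.5 − 13), with a longest arm of 14.8 points. The shortfall arises for any observed rate from 28% to 72% and disappears only outside that range.

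This rests on 50 analysed patients, two-sided 95% intervals, and reading the stated precision as a half-width. Reading it as a bound on each arm would make the shortfall larger. That Wilson was the planning method is an inference from the matching figures, and the conclusion does not depend on it.

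A reader might infer that the trial is too small or that its primary result is compromised. Neither follows: the overall precision holds, and reported intervals will be correct for the data they summarise.

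**What to change.** Keep the sample size and the Clopper-Pearson analysis, and change wording only:

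- Synopsis (statistical methods) and Section 8.2: restate the example as ORR 40%, 95% CI 32.7% to 47.7%.
- Sections 1.5 and 8.2: restate the 50-patient cohort precision as within about ±15%.
- Leave ±8% for 175 patients and ±9% for 125 as rounded figures, and leave the 2.2% zero-event bound.

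The cost is a small text correction and a slightly less favourable stated precision for one cohort. No extra patients are needed and no analysis changes.

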The study was designed to estimate the response rates in patients with T790M mutation positive advanced NSCLC who have progressed on or after EGFR-TKI treatment. ORR will be estimated with 95% exact CIs. With 175 patients the precision of the estimation of ORR in the overall study population will be within +/-8% (e.g. ORR 40%, 95% CI 33.0%, 47.4%). The ORR will also be presented by patient cohort: patients who received previous TKI only; patients who received a TKI and a platinum-based doublet chemotherapy (patients may have also received additional lines of treatment).

Secondary efficacy variables include: DoR, DCR, PFS (according to RECIST 1.1 as assessed by ICR); HRQoL and symptoms; overall survival (OS).

For the primary analysis, ORR will be based on ICR defined visit responses. The imaging scans will be reviewed by two independent radiologists blinded to individual patient data using RECIST 1.1 criteria and will be adjudicated if required. For each patient, the ICR will define the overall visit response data and the relevant scan dates for each time point (i.e. for visits where response or progression is/is not identified). Endpoints (ORR, DoR, DCR, PFS) will be derived from the overall visit response data and the scan dates. Sensitivity analyses of ORR, DoR, DCR and PFS from the investigators assessment will also be performed. The concordance between ORR as assessed by ICR and by investigator will be presented.

The data cut-off for the primary analysis of ORR will take place approximately 3 months after the last subject has been enrolled, to allow opportunity for all patients to complete two RECIST follow-up assessments. At this time, DoR and safety/tolerability will also be summarised. The primary analysis CSR will report the analysis of ORR supported by DoR, and safety and tolerability data.

The full CSR will report the analysis of all primary and secondary endpoints (including updated ORR and DoR, DCR, tumour shrinkage, PFS, OS, Safety, HRQoL, QTc and PK) and summarise the exploratory endpoint of patient reported adverse events (PRO-CTCAE). The data cut-off for this analysis will take place approximately 8 months after the last subject has been enrolled, to allow responding patients to have a DoR greater than 6 months.

Clinical Study Protocol
Drug Substance AZD9291
Study Code D5160C00002
Edition Number 1
Date 26 February 2014

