8.3.2 Evaluable for response analysis set

The evaluable for response analysis set will be all patients who have received at least one dose of treatment and have measurable disease at baseline according to the independent review of baseline imaging data.

The primary analysis of ORR, and other RECIST-based outcomes by independent central review will be produced based on the evaluable for response analysis set. All other efficacy variables will be summarised using the full analysis set.

To support the primary analysis, demographic data will also be summarised for the evaluable for response analysis set

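### The example ORR interval and the ±13% precision for the 50-patient TKI-only cohort do not come from the exact Clopper-Pearson method that the protocol specifies; ±15% is what that method supports

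*Supplement*

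**What the plan says.** The interval method is named twice. The synopsis (Statistical methods) says "ORR will be estimated with 95% exact CIs", and Section 8.9.1 says that ORR by independent central review "will be presented together with 95% exact (Clopper Pearson) confidence intervals".

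The precision figures stand in three places:

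- **Overall:** "With 175 patients the precision of the estimation of ORR in the overall study population will be within +/-8"% (Section 8.2, and the same in the synopsis), with the illustration "e.g. ORR 40%, 95% CI 33.0%, 47.4"%.
- **TKI plus platinum cohort:** "within +/-9% in the 125 patient cohort" (Section 8.2).
- **TKI-only cohort:** "The precision of the estimation of ORR will be within +/-13% in the 50 patient cohort" (Section 8.2).

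Section 1.5 repeats the cohort figures ("9% for multiple therapies; +/-13% for previous TKI only") and gives them as the reason for the size of each cohort. Neither it nor Section 8.2 names the interval method behind the figures. The synopsis also says that ORR will be shown by cohort. Amendments 1 and 2 leave Sections 1.5, 8.2 and 8.9.1 unchanged on these points, so this is current text.

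**The concern.** In the synopsis the example interval follows directly on the statement that exact intervals will be used, so a reader takes it to be exact. It is narrower than an exact interval at 70/175. If the planning figures were computed by a less conservative method than the one used for analysis, each of them needs checking against the specified method, and the smallest cohort is where the difference is largest.

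This is a single-arm estimation study without a hypothesis test, so interval width is the only reason given for choosing 50 and 125 patients. If the specified method does not deliver the stated width, the justification for that cohort is wrong as written, and the report will show a wider interval than the protocol led readers to expect.

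**Working it through.** **Inputs.** n = 175, 125 and 50 (Section 8.2); ORR 40% (example in the synopsis and Section 8.2); ORR 50% (the phase I rate in T790M-positive patients cited in Section 1.3); two-sided 95% confidence.

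**Step 1: reproduce the protocol's example.** With p = 0.40, n = 175, z = 1.96 and z² = 3.8415, the Wilson score interval is

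- centre = (p + z²/2n) / (1 + z²/n) = (0.4 + 0.01098) / 1.02195 = 0.4021
- half-width = z·√[p(1−p)/n + z²/4n²] / (1 + z²/n) = 1.96 × √(0.0013714 + 0.0000314) / 1.02195 = 0.0718
- interval = 33.0% to 47.4%

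This is the stated interval to the decimal. (Agresti-Coull is practically the same.) The Wald interval is 32.7% to 47.3%.

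**Step 2: the specified method.** For x responders among n, the Clopper-Pearson limits are beta quantiles: lower = Beta(0.025; x, n−x+1), upper = Beta(0.975; x+1, n−x).

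| x/n | ORR | Exact 95% CI | Half-width | Lower / upper arm | Stated |
|---|---|---|---|---|---|
| 70/175 | 40% | 32.7% to 47.7% | 7.5 | −7.3 / +7.7 | ±8% |
| 50/125 | 40% | 31.3% to 49.1% | 8.9 | −8.7 / +9.1 | ±9% |
| 20/50 | 40% | 26.4% to 54.8% | 14.2 | −13.6 / +14.8 | ±13% |
| 25/50 | 50% | 35.5% to 64.5% | 14.5 | −14.5 / +14.5 | ±13% |

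**Step 3: worst case over all possible response counts.**

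| n | Largest half-width | Longest single arm | Stated |
|---|---|---|---|
| 175 | 7.64 | 7.69 | ±8%: holds |
| 125 | 9.07 | 9.16 | ±9%: holds after rounding |
| 50 | 14.47 | 14.83 | ±13%: missed |

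For n = 50 the half-width exceeds 13 points for 14 to 36 responders, that is, an observed ORR of 28% to 72%.

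**Step 4: where ±13% may have come from.** At 20/50 the Wilson half-width is 13.1, which rounds to 13, and at 25/50 it is 13.4. The Wald half-widths are 13.6 and 13.9. So ±13% agrees with the method that produced the example interval, after rounding, but not with the exact method.

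**Step 5: size of the shortfall in patients.** Under the exact method at 40% ORR, ±13 points needs about 60 patients on half-width (24/60 gives 12.95) and about 65 on the longer arm (26/65 gives 12.9).

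**The case against.** The strongest reply is that this is one method mismatch and not several wrong numbers: all the figures fit a Wilson calculation rounded to whole points, and nothing hangs on them. There is no test, threshold or go/no-go rule tied to the widths. The primary analysis is the overall evaluable set, whose ±8% is met. Section 8.9.1 fixes the analysis method clearly, so the reported intervals will be right whatever Section 8.2 says. All of this stands, and it limits the consequence. It does not make the stated ±13% true under the method the protocol names.

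A reader might infer two stronger points that the documents do not support:

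- **That the 125-patient cohort also fails.** It does so only if precision is read as the distance to the farther limit, and then by at most 0.16 point (9.16 against 9). The protocol does not define precision that way. The exact half-width is 8.9 at 40% and at most 9.07, so a figure stated as a whole number is essentially met.
- **That losses from the primary analysis set undo the overall ±8%.** The set is limited to patients who "have measurable disease at baseline according to the independent review of baseline imaging data", so some loss through disagreement between site and central readers is possible. But inclusion criterion 9 already requires a measurable lesion, and the documents give no non-evaluable rate. Any assumed rate would be the reader's own.

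Nor is the whole sample-size rationale in doubt. The overall size also rests on safety, which this point does not touch.

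**Conclusion.** The point holds for two items. The example interval is a Wilson interval in a plan that specifies exact ones; the difference is 0.3 point at each end. The ±13% for the TKI-only cohort is not delivered by the specified method: the half-width is 14.2 points at 40% and 14.5 at 50%, with an arm of up to 14.8. The ±9% and ±8% statements can stand.

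This assumes that all 50, 125 and 175 planned patients enter the analysis and that ± is read as the half-width of a two-sided 95% interval. Reading it as the farther limit makes the 50-patient shortfall larger, not smaller. The matter deserves correction because precision is the stated reason for the cohort size, but it affects no decision rule and no planned analysis.

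**What to change.** - In the synopsis and Section 8.2, restate the example for 40% ORR with 175 patients as 32.7% to 47.7%.
- In Sections 1.5 and 8.2, restate the TKI-only cohort precision as within about ±15%, which covers the longest exact arm (14.8) at any ORR.
- Leave ±9% for the 125-patient cohort and ±8% overall unchanged.

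The cost is wording and a slightly less favourable stated precision for the TKI-only cohort. No extra patients are needed and the planned analysis does not change.

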8.3 Definitions of analysis sets

8.3.1 Full analysis set

The full analysis set is defined as all patients enrolled who received at least one dose of investigational product.

Safety data summaries and analyses will be produced based on the full analysis set.

8.3.2 Evaluable for response analysis set

The evaluable for response analysis set will be all patients who have received at least one dose of treatment and have measurable disease at baseline according to the independent review of baseline imaging data.

The primary analysis of ORR, and other RECIST-based outcomes by independent central review will be produced based on the evaluable for response analysis set. All other efficacy variables will be summarised using the full analysis set.

To support the primary analysis, demographic data will also be summarised for the evaluable for response analysis set

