8.4 Outcome measures for analyses

Independent Central Review of RECIST based assessments

The Independent Central Review of all radiological imaging data will be carried out using RECIST version 1.1. All radiological scans for all patients (including those at unscheduled visits, or outside visit windows) will be provided to the ICR. Prior radiotherapy reports for patients (at baseline) and information on biopsied lesions will also be provided to the ICR to allow the selection of appropriate target lesions. The imaging scans will be reviewed by two independent radiologists using RECIST 1.1 criteria and will be adjudicated if required. For each patient, the ICR will define the overall visit response data (CR, PR, SD, PD or NE) and the relevant scan dates for each time point (i.e. for visits where response or progression is/is not identified). If a patient has had a tumour assessment which cannot be evaluated then the patient will be assigned a visit response of not evaluable (NE) (unless there is evidence of progression in which case the response will be assigned as PD). Endpoints (ORR, DoR, DCR, PFS) will be derived from the overall visit response date and the scan dates. ORR will only include patients whose response has been confirmed by a second scan at least 4 weeks after the initial response. The endpoint of tumour shrinkage will be assessed from tumour size measurements based on the primary independent radiologist assessment.

Further details of the Independent Central Review will be documented in the Independent Review Charter.

Investigator RECIST based assessments

From the investigators review of the imaging scans, the RECIST tumour response data will be used to determine each subject's visit response according to RECIST version 1.1.

At each visit, patients will be programmatically assigned a RECIST 1.1 visit response of CR, PR, SD or PD depending on the status of their disease compared with baseline and previous assessments. If a patient has had a tumour assessment which cannot be evaluated then the patient will be assigned a visit response of not evaluable (NE) (unless there is evidence of progression in which case the response will be assigned as PD).

Please refer to [Appendix D](#) for the definitions of CR, PR, SD and PD.

Overall Response Rate (ORR)

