8.9.2 Analysis of the secondary variable(s)

Duration of response

Duration of response in responding patients will be summarised and the number (%) of responding patients with a duration of response >3; >6; >9; >12 months will be presented. A

Kaplan Meier plot and median duration of response with 95% CI (calculated from the Kaplan Meier plot) will be presented. DCR will be summarised. DoR and DCR will be presented based on the ICR, and as a sensitivity analysis they will be present based on the investigator assessment.

Tumour shrinkage

The best absolute change in target lesion tumour size from baseline and percentage change in target lesion tumour size from baseline will be summarized using descriptive statistics and presented at each timepoint.

Tumour size will also be presented graphically using waterfall plots, to present each patient's best percentage change in tumour size as a separate bar, with the bars ordered from the largest increase to the largest decrease. Reference lines at the +20% and -30% change in tumour size levels will be added to the plots, which correspond with the definitions of progression and 'complete or partial' response respectively.

The mean and median best change from baseline in tumour size will be summarized. This will also be summarised for week 6 and week 12 data.

To assess the depth of tumour shrinkage, the proportion of patients who achieve >30%, >50% and >75% reduction in target lesions will be summarised descriptively.

Tumour shrinkage will be presented based on the primary reader ICR data, and as a sensitivity analysis they will be present based on the investigator assessment.

Progression Free Survival (PFS)

PFS will be displayed using a Kaplan-Meier plot. The number events, median (calculated from the Kaplan Meier plot), and the proportion of patients without an event at 6, 12 and 18 months summarised. PFS will be presented based on the ICR assessments, and as a sensitivity analysis PFS will be presented based on the investigator assessment.

Overall Survival (OS)

When there is sufficient data (>20 events), OS will be displayed using a Kaplan-Meier plot. The number events, median (calculated from the Kaplan Meier plot), and the proportion of patients without an event at 6, 12 and 18 months will be summarised.

As appropriate, summaries of the number and percentage of patients who have died, are still in survival follow-up, are lost to follow-up and have withdrawn consent will be presented.

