4.6 Evaluation of Overall Visit Response

The overall visit response will be derived using the algorithm shown in [Table 4](#).

Table 4 Overall Visit Response

Target lesions	Non-Target lesions	New Lesions	Overall response
CR	CR	No	CR
CR	NA	No	CR
CR	Non-CR/Non PD	No	PR
CR	NE	No	PR
PR	Non PD or NE	No	PR
SD	Non PD or NE	No	SD
NA	Non CR/Non PD	No	SD (Non CR/non PD)
NE	Non-PD or NE	No	NE
NA	NE	No	NE
PD	Any	Yes or No	PD
Any	PD	Yes or No	PD
Any	Any	Yes	PD

CR = complete response, PR = partial response, SD = stable disease, PD = progressive disease
IR = incomplete response, NE = not evaluable, NA = not applicable (relevant when no NTLs at baseline)

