8.4 Outcome measures for analyses

Previous text:

Progression Free Survival (PFS)

PFS is defined as the time from enrolment until the date of objective disease progression or death (by any cause in the absence of progression) regardless of whether the patient withdraws from study therapy or receives another anti-cancer therapy prior to progression. Patients who have not progressed or died at the time of analysis will be censored at the time of the latest date of assessment from their last evaluable RECIST assessment.

Revised text:

Progression Free Survival (PFS)

PFS is defined as the time from **date of first dose** until the date of objective disease progression or death (by any cause in the absence of progression) regardless of whether the patient withdraws from study therapy or receives another anti-cancer therapy prior to

progression. Patients who have not progressed or died at the time of analysis will be censored at the time of the latest date of assessment from their last evaluable RECIST assessment.

Section of protocol affected:

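### ICR-based PFS, the main PFS analysis, is confined to patients with ICR-measurable disease, although neither progression nor death depends on measurability

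*Supplement*

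**What the plan says.** Section 8.3.2 of the protocol, which neither amendment changes, assigns the sets in two sentences. The first is "The primary analysis of ORR, and other RECIST-based outcomes by independent central review will be produced based on the evaluable for response analysis set". The second is "All other efficacy variables will be summarised using the full analysis set". To enter the evaluable-for-response set a patient must have been dosed and "have measurable disease at baseline according to the independent review of baseline imaging data". The full analysis set has no such condition: "The full analysis set is defined as all patients enrolled who received at least one dose of investigational product" (section 8.3.1).

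PFS is one of the ICR outcomes. Under the heading on independent central review, section 8.4 says: "Endpoints (ORR, DoR, DCR, PFS) will be derived from the overall visit response date and the scan dates". Section 8.9.2 makes the ICR version the main one: "PFS will be presented based on the ICR assessments, and as a sensitivity analysis PFS will be presented based on the investigator assessment". As amended by Amendment 2, PFS runs from first dose "until the date of objective disease progression or death (by any cause in the absence of progression", and its definition says nothing of measurable disease.

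Section 8.9.5 says that the investigator-based analyses of ORR, DoR, DCR and PFS follow the same methods, without naming an analysis set.

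**The concern.** A PFS curve from a single-arm study is read as the experience of everyone who was treated. Section 8.3.2 instead selects patients by whether the central readers found a lesion they could measure at baseline. That condition belongs to response: a partial response is a 30% fall in a sum of diameters and cannot be called without target lesions. It has no role in deciding that a patient has progressed through a new lesion or non-target disease, or has died.

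Three things are at stake:

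- Some treated patients and their PFS events are left out of the main PFS analysis, while their deaths stay in OS on the full analysis set. PFS and OS then describe slightly different groups.
- If investigator PFS is on the full analysis set, the sensitivity analysis changes assessor and population together, and a difference from ICR PFS cannot be put down to the readers.
- If investigator PFS is on the evaluable set, no PFS analysis covers all treated patients.

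**Working it through.** The plan gives no figure on this point to reproduce. The check sets the provisions side by side and then gives a scale under stated assumptions.

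**Is PFS covered by the restriction?** Yes. Section 8.3.2 covers RECIST-based outcomes by ICR, section 8.4 lists PFS among them, and section 8.9.2 presents PFS by ICR. The introduction to section 8.9 mentions both sets and leaves the choice to what is appropriate. That general wording does not displace the explicit assignment in section 8.3.2.

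**Does a PFS event need measurable disease?** No.
- Section 8.4 (ORR) builds measurable disease into the definition of ORR; the PFS definition does not.
- Appendix D section 4.4 counts any new lesion as progression.
- Appendix D section 4.3.1 defines non-target progression and has a note for patients without target lesions at baseline.
- Appendix D Table 4 has rows with target lesions not applicable, one of them yielding "SD (Non CR/non PD"). Its rows for non-target progression and for new lesions apply whatever the target-lesion status.
- Death needs no lesion.

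**Can a treated patient fall outside the evaluable set?** Yes. Criterion 9 (section 3.1) is judged at the site. The ICR chooses its own target lesions with the help of radiotherapy and biopsy information (section 8.4), and Appendix D section 2 treats irradiated and screening-biopsied lesions as non-measurable. The patients left out are those in whom the ICR disagrees with the site or has no usable baseline imaging.

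**How many?** Planned N is about 175 (section 8.2). The share *f* left out is not in the documents, so a range is assumed:

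| f (assumed) | 175 × f | Patients, rounded |
|---|---|---|
| 1% | 1.75 | 2 |
| 3% | 5.25 | 5 |
| 5% | 8.75 | 9 |
| 10% | 17.5 | 18 |

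**What could that do to a PFS rate?** Treat the rate at a fixed time as a mixture of the two groups, ignoring differences in censoring:

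rate in all treated = (1 − f) × S_in + f × S_out

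The evaluable set reports S_in, so

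error = S_in − rate in all treated = f × (S_in − S_out).

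Assume S_in between 50% and 70% and S_out between 20% and 90%; neither is in the documents. The extremes come from S_in = 50% with S_out = 90% (difference −40 points) and S_in = 70% with S_out = 20% (difference +50 points):

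| f | Lowest error (points) | Highest error (points) |
|---|---|---|
| 1% | 0.01 × (−40) = −0.4 | 0.01 × 50 = +0.5 |
| 3% | −1.2 | +1.5 |
| 5% | −2.0 | +2.5 |
| 10% | −4.0 | +5.0 |

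The sign depends on whether the excluded patients do better or worse than the rest, which cannot be known in advance.

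**The case against.** The case for leaving the plan alone has real substance.

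- **Size.** Criterion 9 requires a measurable lesion, neither irradiated nor chosen for biopsy, and section 3 allows no exceptions. A reader might infer that 5-10% of patients are lost; nothing in the documents supports that share, and the lower end of the range is more plausible. This stands.
- **Events recovered.** A reader might infer that every PFS event of an excluded patient would come back on the full analysis set. Section 8.4 does not support this: patients with no baseline data or no evaluable visits are censored at day 0 unless they die within two visits of baseline. The change adds full follow-up only for patients whose baseline scan the ICR can read but who have no measurable lesion on it. This stands.
- **Population mismatch.** A reader might infer that ICR and investigator PFS certainly use different patients. Section 8.9.5 leaves that open. This stands as a limit on the claim, but it does not rescue the plan: on one reading assessor and population change together, and on the other no PFS analysis covers all treated patients.
- **Reading rules.** Appendix D section 1 limits that appendix to investigator assessment. Further ICR detail sits in the Independent Central Review Charter, which is not shown, so Table 4 cannot be assumed to govern the ICR. Table 4 also has no row for target lesions not applicable with non-target complete response. This stands and shapes the fix. It does not make progression depend on measurability, since section 5.1.1 applies RECIST 1.1 to both reviews.
- **Consequence.** PFS is secondary and descriptive here, with no test or sample-size claim resting on it, and a single set for all ICR outcomes lets them be read together. This lowers the weight but gives no reason to prefer the narrower population for PFS.

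The SAP is also not shown. The point rests on an explicit assignment in the protocol, not on something left for the SAP to supply.

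**Conclusion.** The point holds for ICR-based PFS. On the current text, the main PFS analysis omits dosed patients without ICR-measurable disease at baseline, for a reason that bears on response and tumour shrinkage but not on progression or death. The effect is probably small. Its size rests on an assumed share of 1-10% and on assumed PFS rates, and its direction is unknown. The set for investigator PFS is ambiguous and needs stating whichever reading was intended.

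The point does not reach the primary endpoint, for which the measurable-disease condition is proper. Nor are the omitted patients lost to the study report: their deaths remain in OS, and section 8.3.2 read alone keeps them in investigator PFS.

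**What to change.** Amend section 8.3.2 so that the evaluable-for-response set is used for ICR ORR, DoR and tumour shrinkage, and PFS by ICR, PFS by investigator and OS all use the full analysis set. Name the set for investigator PFS in section 8.9.5 as well. DCR need not move to resolve this point.

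Have the ICR Charter state that patients without ICR target lesions are assessed for progression on non-target and new lesions under RECIST 1.1. Leave the section 8.4 rule for patients with no baseline data or no evaluable visits as it is.

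The cost is a short change to the protocol and SAP, and possibly a line in the Charter. No further imaging is needed, because sections 5.1.2 and 8.4 already send all scans from all patients to the ICR. The small downside is that ICR PFS and ICR ORR would have slightly different denominators. ICR PFS on the evaluable set can be kept as a supportive summary for readers who want the two side by side.
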